6.1.7 AEs of special interest

6.1.7.1 Hy's Law

Potential Hy's Law cases will be summarized with the LFT lab data. The following definition will be used:

- [AST $\geq 3 \times \text{ULN}$ or ALT $\geq 3 \times \text{ULN}$] and Total Bilirubin $\geq 2 \times \text{ULN}$ in the absence of ALP (Alkaline phosphatase) $\geq 2 \times \text{ULN}$

In order to meet the above criteria, a subject must experience the elevation in bilirubin and ALT or AST (and the absence of ALP elevation) at the same visit. For example, a subject who experiences a $\geq 2 \times \text{ULN}$ elevation of bilirubin at one visit and a $\geq 3 \times \text{ULN}$ elevation in ALT (or AST) at a subsequent visit has not fulfilled the Hy's law criteria. Follow-up information should be reported if an alternative etiology is identified during investigation and monitoring of the participant.

6.1.8 Other AEs

6.1.8.1 Anaphylaxis

The SMQ *Anaphylactic reaction* consists of three parts:

1. A **narrow search** containing PTs that represent core anaphylactic reaction terms (Category A – core anaphylactic reaction terms)
 - Anaphylactic reaction
 - Anaphylactic shock
 - Anaphylactic transfusion reaction
 - Anaphylactoid reaction
 - Anaphylactoid shock
 - Circulatory collapse
 - Dialysis membrane reaction
 - Kounis syndrome
 - Procedural shock
 - Shock
 - Shock symptom
 - Type I hypersensitivity
2. A **broad search** that contains additional terms that are added to those included in the narrow search. These additional terms are signs and symptoms possibly indicative of anaphylactic reaction and categorized in B, C, or D.
 - Category B (Upper Airway/Respiratory terms)
 - Acute respiratory failure

-
- Asthma
 - Bronchial oedema
 - Bronchospasm
 - Cardio-respiratory distress
 - Chest discomfort
 - Choking
 - Choking sensation
 - Circumoral oedema
 - Cough
 - Cough variant asthma
 - Cyanosis
 - Dyspnoea
 - Hyperventilation
 - Irregular breathing
 - Laryngeal dyspnoea
 - Laryngeal oedema
 - Laryngospasm
 - Laryngotracheal oedema
 - Mouth swelling
 - Nasal obstruction
 - Oedema mouth
 - Oropharyngeal oedema
 - Oropharyngeal spasm
 - Oropharyngeal swelling
 - Pharyngeal oedema
 - Pharyngeal swelling
 - Respiratory arrest
 - Respiratory distress
 - Respiratory failure
 - Reversible airways obstruction
 - Sensation of foreign body

-
- Sneezing
 - Stridor
 - Swollen tongue
 - Tachypnoea
 - Throat tightness
 - Tongue oedema
 - Tracheal obstruction
 - Tracheal oedema
 - Upper airway obstruction
 - Wheezing
 - Category C (Angioedema/Urticaria/Pruritus/Flush terms)
 - Acquired C1 inhibitor deficiency
 - Allergic oedema
 - Angioedema
 - Circumoral swelling
 - Erythema
 - Eye oedema
 - Eye pruritus
 - Eye swelling
 - Eyelid oedema
 - Face oedema
 - Flushing
 - Hereditary angioedema with C1 esterase inhibitor deficiency
 - Injection site urticaria
 - Lip oedema
 - Lip swelling
 - Nodular rash
 - Ocular hyperaemia
 - Oedema
 - Oedema blister
 - Periorbital oedema

-
- Periorbital swelling
 - Pruritus
 - Pruritus allergic
 - Rash
 - Rash erythematous
 - Rash pruritic
 - Skin swelling
 - Swelling
 - Swelling face
 - Swelling of eyelid
 - Urticaria
 - Urticaria papular
 - Category D (Cardiovascular/Hypotension terms)
 - Blood pressure decreased
 - Blood pressure diastolic decreased
 - Blood pressure systolic decreased
 - Cardiac arrest
 - Cardio-respiratory arrest
 - Cardiovascular insufficiency
 - Diastolic hypotension
 - Hypotension
 - Hypotensive crisis
 - Post procedural hypotension
 - 3. An **algorithmic approach** which combines a number of anaphylactic reaction symptoms in order to increase specificity. A case must include one of the following where both occur on either the same day as when an injection was administered or one day after, and for scenarios where two must have been reported, both events must have occurred within one day of each other (as anaphylaxis is an acute event, imputed dates should not be used in the algorithmic approach):
 - A narrow term or a term from Category A
 - A term from Category B – (Upper Airway/Respiratory) AND a term from Category C – (Angioedema/Urticaria/Pruritus/Flush)

- A term from Category D – (Cardiovascular/Hypotension) AND [a term from Category B – (Upper Airway/Respiratory) OR a term from Category C – (Angioedema/Urticaria/Pruritus/Flush)]

6.1.9 Potentially clinically significant criteria for safety endpoints

6.1.9.1 Marked abnormality criteria for laboratory data

Markedly abnormal values are defined as those with a severity of Grade 3 and above based on the common terminology criteria for adverse events (CTCAE). Assessed labs and definitions of markedly abnormal values using the Grade 3 cut points are given below.

Note that participants who meet the decreased potassium criterion of 3.0 to <LLN, which is specified as the decreased potassium lab criterion for both CTCAE Grade 1 and Grade 2, will be counted as Grade 2.

The following tables lists lab assessments and abnormal value cutoffs for this study.

Table 6–1: Laboratory Assessments

Laboratory assessments	Parameters			
Hematology	Platelet Count	RBC Indices: MCV MCH %Reticulocytes		WBC Count with Differential: Neutrophils Lymphocytes Monocytes Eosinophils Basophils
	RBC Count			
	Hemoglobin			
	Hematocrit			
Clinical Chemistry ^a	Blood Urea Nitrogen	Potassium	AST/serum glutamic-oxaloacetic transaminase	Total and direct bilirubin
	Creatinine	Sodium	ALT/serum glutamic-pyruvic transaminase	Total Protein
	Glucose (nonfasting)	Calcium	Alkaline phosphatase	
Routine Urinalysis	
 Specific gravity pH, glucose, protein, blood, ketones, bilirubin, urobilinogen, nitrite, and leukocyte esterase by dipstick Microscopic examination (if blood or protein is abnormal) 			
Other Screening Tests	
 Serum human chorionic gonadotropin (hCG) pregnancy test (as needed for women of childbearing potential) by central laboratory at Screening and urine pregnancy test locally for all assessments after Screening (or at home during the OLE Period) IGRA testing Serology (HBsAg and hepatitis C virus antibody) Plasma sample for HIV antibody assessment The results of each test must be entered into the eCRF.			

ALT=alanine aminotransferase; AST=aspartate aminotransferase; BUN=blood urea nitrogen; eCRF=electronic Case Report Form; HBsAg=hepatitis B surface antigen; HIV=human immunodeficiency virus; INR=international normalized ratio; MCH=mean corpuscular hemoglobin; MCV=mean corpuscular volume; RBC=red blood cell count; ULN=upper limit of normal; WBC=white blood cell count

^a Details of liver chemistry stopping criteria and required actions and follow-up assessments after liver stopping or monitoring event are given in protocol. All events of ALT $\geq 3 \times \text{ULN}$ and bilirubin $\geq 2 \times \text{ULN}$ ($>35\%$ direct bilirubin) or ALT $\geq 3 \times \text{ULN}$ and INR >1.5 , if INR measured, may indicate severe liver injury (possible Hy's Law) and must be reported as an SAE (excluding studies of hepatic impairment or cirrhosis).

Table 6–2: Definitions of Markedly Abnormal Haematology Values

Parameter name	Conventional		Standard		Abnormal Designation
	Unit	Criteria	Unit	Criteria	
Hemoglobin	g/dL	<8.0 >4.0 above ULN or Baseline if Baseline > ULN	g/L	<80 >40 above ULN or Baseline if Baseline > ULN	AL AH
Lymphocytes Absolute	10 ⁹ /L	<0.5 >20.0	10 ⁹ /L	<0.5 >20.0	AL AH
Neutrophils Absolute	10 ⁹ /L	<1.0	10 ⁹ /L	<1.0	AL
Platelets	10 ⁹ /L	<50	10 ⁹ /L	<50	AL
WBC/Leukocytes	10 ⁹ /L	<2.0 >100	10 ⁹ /L	<2.0 >100	AL AH

AH=abnormal high, AL=abnormal low, dL=deciliter, g=gram, L=liter, ULN=upper limit of normal, WBC=white blood cells. ULN will be sourced from lab.

Table 6–3: Definitions of Markedly Abnormal Biochemistry Values

Parameter name	Conventional		Standard		Abnormal Designation
	Unit	Criteria	Unit	Criteria	
Creatinine	mg/dL	>3.0 x ULN or Baseline if Baseline > ULN	µmol/L	>3.0 x ULN or Baseline if Baseline > ULN	AH
Glucose	mg/dL	<40 >250	mmol/L	<1.7 >13.9	AL AH
Calcium	mg/dL	>12.5 <7.0	mmol/L	>3.1 <1.75	AH AL
Magnesium	mg/dL	>3.0 <0.9	mmol/L	>1.23 <0.4	AH AL
Potassium	mmol/L	>6.0 <3.0	mmol/L	>6.0 <3.0	AH AL
Sodium	mmol/L	>155 <130	mmol/L	>155 <130	AH AL

AH=abnormal high, AL=abnormal low, dL=deciliter, L= liter, LLN=lower limit of normal, mg=milligram, mmol=millimole, ULN=upper limit of normal. ULN/LLN will be sourced from lab. Participants who meet the decreased potassium criterion of 3.0-<LLN, which is specified as the decreased potassium lab criterion for both CTCAE Grade 1 and Grade 2, will be counted as Grade 2.

Table 6–4: Definitions of Markedly Abnormal Liver Function Tests

Parameter name	Conventional		Standard		Abnormal Designation
	Unit	Criteria	Unit	Criteria	
ALP	U/L	>5.0 x ULN	U/L	>5.0 x ULN	AH
ALT	U/L	>5.0 x ULN	U/L	>5.0 x ULN	AH
AST	U/L	>5.0 x ULN	U/L	>5.0 x ULN	AH
Total Bilirubin	mg/dL	>3.0 x ULN	μmol/L	>3.0 x ULN	AH
GGT	U/L	>5.0 x ULN	U/L	>5.0 x ULN	AH

AH=abnormal high, AL=abnormal low, ALT=alanine aminotransferase, ALP = alkaline phosphatase, AST=aspartate aminotransferase, dL=deciliter, GGT=gamma-glutamyl transferase, L=liter, mg=milligram; μmol=micromole, ULN=upper limit of normal. ULN will be sourced from lab.

6.1.9.2 Marked abnormality criteria for vital signs

The marked abnormality criteria for blood pressure are provided in the table below:

Table 6–5: Definitions of Markedly Abnormal Vital Signs

Parameter (unit)	Age group	Markedly Abnormal Low	Markedly Abnormal High
Systolic blood pressure (mmHg)	≤17	<90 or a decrease from Baseline of ≥30%	>5 above the 99 th percentile
	>17	<90 or a decrease from Baseline of ≥30%	>160 or an increase from Baseline of ≥30%
Diastolic blood pressure (mmHg)	≤17	<50 or decrease of ≥20% from Baseline	>5 above the 99 th percentile
	>17	<50 or decrease of ≥20% from Baseline	>105

The values of the 99th percentile of systolic and diastolic blood pressure values, by age, sex and height percentile are provided in Section 6.3.3 for participants aged 17 or less.

6.1.10 Compliance

Study treatment compliance will be calculated and summarized in the SS.

Treatment compliance will be calculated as:

$$(\text{Actual number of completed injections} / \text{Expected number of injections}) \times 100$$

For participant who permanently discontinues IMP, the number of expected injections is based on the time of early discontinuation relative to the dosing visits.

Compliance will be summarized descriptively by weight-categorized dose group and overall, for each study periods separately and combined. The number and percentage of participants meeting certain compliance thresholds (<75% and ≥75%) will also be reported.

6.2 Appendix 2: Changes to Protocol-Planned Analyses

The following have been added to the SAP, but are not present in the Protocol:

- The COVID-19 impact analysis (Section 5.2.1) has been added.
- The definition of analysis sets has been changed (Section 4.1):
 - Immunogenicity analyses will be based on SS or OLS, and participants will be summarized as randomized.
 - Pharmacokinetic variables will be analyzed for all participants in the PK-PPS and will be summarized as randomized.
 - OLS analyses will be based on the SS and as treated.
 - For summaries using both PK-PPS and OLS, participants will be summarized as randomized.
- Multiple imputation is no longer being applied to missing continuous data. Instead, the LOCF method will be used to impute the missing value (Section 5.1.1.7.3).
- Shift tables for growth assessments for height and weight (Section 5.6.3.6.2) have been added.

6.3 Appendix 3: Percentiles Derivation and Growth Charts

This appendix describes the approach used to derive age and sex-specific percentiles for BMI, weight, and height from LMS parameters available in published growth charts. The LMS parameters are the smoothed skew (L), the median (M), and the coefficient of variation (S).

Additionally, this appendix provides the 99th percentile values for systolic and diastolic blood pressure by age, sex and height percentile. These values will be used to identify markedly abnormal values for participants aged ≤17 years.

6.3.1 Derivation of percentiles from LMS parameters

The L, M, and S parameters from growth charts for BMI, height, and weight, by age and sex, are provided in Section 6.3.2.

Deriving the percentile value of a given measurement, for a given participant is done in 3 steps (Cole, 1990):

1. From the growth chart of the measurement of interest (BMI, height, or weight), identify the L, M, and S parameters corresponding to the participant sex and age (at the time of the measurement).
2. Calculate the z-score for the measurement using the following formula:

$$z = \frac{\left[\left(\frac{X}{M}\right)^L - 1\right]}{L \times S}$$

Where X is the measurement value and L, M, and S are the parameters identified in step 1.

3. The calculated z-score is then converted to the percentile value using the cumulative distribution function from the standard normal distribution.

6.3.2 Growth charts

6.3.2.1 Growth chart for BMI by age and sex

The BMI growth chart (CDC, 2000) provides the L, M, and S parameters by age and sex, where the age is provided in months at the half-month point. For example, 78.5 months represents the interval [78.0, 79).

In this study, age is recorded in years at each visit where the weight and height are recorded. In the BMI growth chart, the L, M, and S parameters for each age in years were mapped to the chart values corresponding to the half-year time point for that year, with respect to sex. For example, LMS values for a 12 year-old correspond to the half-year timepoint of $12.5 \times 12 = 150$ months, that is the interval [150.0, 151.0) represented by 150.5 months in the chart.

Table 6–6: Growth Chart for BMI¹ (kg/m²) by Age and Sex

Sex	Age (years)	Month in the chart	L	M	S
Male	12	150.5	-2.385858029	18.1387275	0.132990575
Male	13	162.5	-2.277017201	18.81201584	0.134879611
Male	14	174.5	-2.179425674	19.50672885	0.135308594
Male	15	186.5	-2.085574403	20.20858236	0.134718085
Male	16	198.5	-1.993150137	20.90294449	0.1336202
Male	17	210.5	-1.908831065	21.57417053	0.132584784
Female	12	150.5	-1.959520079	18.42002284	0.149783482
Female	13	162.5	-1.9610997	19.04811118	0.151176355
Female	14	174.5	-2.002014224	19.64746266	0.151009595
Female	15	186.5	-2.074459502	20.19980767	0.14984254
Female	16	198.5	-2.167044578	20.6891237	0.148349348
Female	17	210.5	-2.26238209	21.10163241	0.147323144

BMI=body mass index

¹ Centers for Disease Control and Prevention (2000). https://www.cdc.gov/growthcharts/percentile_data_files.htm

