5.6.3.6.2 Growth assessment

Descriptive statistics for height and weight change from baseline will be reported by weight-categorized dose group over time. Growth percentiles will be calculated for height, weight, and body mass index (BMI) at Week 16, Week 64, and Week 124. A shift table of the number and percentage of participants falling in each percentile category from baseline to these post-baseline visits will be presented by weight-categorized dose group. The percentile categories are listed below.

- Height (percentile):
 - $<5^{\text{th}}$
 - $\geq 5^{\text{th}}$ to $<25^{\text{th}}$
 - $\geq 25^{\text{th}}$ to $<50^{\text{th}}$
 - $\geq 50^{\text{th}}$ to $<75^{\text{th}}$
 - $\geq 75^{\text{th}}$ to $<95^{\text{th}}$
 - ≥ 95
- Weight (percentile): the same percentile categories as height
- BMI (percentile):
 - $<5^{\text{th}}$ (underweight)
 - $\geq 5^{\text{th}}$ to $<85^{\text{th}}$ (normal or healthy weight)
 - $\geq 85^{\text{th}}$ to $<90^{\text{th}}$ (overweight)
 - $\geq 90^{\text{th}}$ to $<95^{\text{th}}$ (overweight)
 - $\geq 95^{\text{th}}$ to $<97^{\text{th}}$ (obese)
 - $\geq 97^{\text{th}}$ (obese)

Height and weight percentile reference levels are provided in Section 6.3.2.

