6.3.2.2 Growth chart for height by age and sex

Similar to the BMI growth chart, the height growth chart (CDC, 2009) provides the L, M, and S parameters by age and sex, where the age is provided in months at the half-month point.

In the Growth Chart for Height, the L, M, and S parameters for each age in years were mapped to the chart values corresponding to the half-year time point for that year, with respect to sex.

Table 6–7: Growth Chart for Height¹ (cm) by Age and Sex

Sex	Age (years)	Month in the chart	L	M	S
Male	12	150.5	0.531951655	152.6623878	0.050273285
Male	13	162.5	1.232768816	160.3493168	0.049926861
Male	14	174.5	2.016781776	167.4641466	0.047506783
Male	15	186.5	2.2253265	172.1562865	0.044362674
Male	16	198.5	1.927320937	174.6309856	0.042107465
Male	17	210.5	1.543252982	175.8359757	0.040938463
Female	12	150.5	1.358162799	154.755501	0.046198356
Female	13	162.5	1.076970655	159.2074654	0.042114211
Female	14	174.5	0.902452436	161.3267744	0.040409354
Female	15	186.5	0.913397733	162.2908474	0.039913066
Female	16	198.5	0.971038162	162.7718741	0.03976685
Female	17	210.5	1.025142554	163.0401953	0.039706971

¹ Centers for Disease Control and Prevention (2009). https://www.cdc.gov/growthcharts/percentile_data_files.htm

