6.3.2.3 Growth chart for weight by age and sex

In the Growth Chart for Weight, the L, M, and S parameters for each age in years were mapped to the chart values corresponding to the half-year time point for that year, with respect to sex.

Table 6–8: Growth Chart for Weight¹ (kg) by Age and Sex

Sex	Age (years)	Month in the chart	L	M	S
Male	12	150.5	-0.76027	43.18828	0.197464
Male	13	162.5	-0.65414	48.51113	0.194344
Male	14	174.5	-0.63492	53.91261	0.186442
Male	15	186.5	-0.72322	58.90293	0.176887
Male	16	198.5	-0.89044	63.03228	0.168655
Male	17	210.5	-1.0354	66.10749	0.163439
Female	12	150.5	-0.85031	43.96612	0.200419
Female	13	162.5	-1.00305	47.83661	0.19333
Female	14	174.5	-1.23801	50.92541	0.183328
Female	15	186.5	-1.51816	53.13327	0.172761
Female	16	198.5	-1.76224	54.61224	0.164368

Female	17	210.5	-1.86898	55.70624	0.160423
--------	----	-------	----------	----------	----------

¹ Centers for Disease Control and Prevention (2009). https://www.cdc.gov/growthcharts/percentile_data_files.htm

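### Growth percentile shift tables score whole-year age on one mid-year reference row and have no rule for age 18 or over, so some category changes are artefacts and some participants cannot be scored

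*SAP*

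**What the plan says.** SAP 5.6.3.6.2 plans the output: "Growth percentiles will be calculated for height, weight, and body mass index (BMI) at Week 16, Week 64, and Week 124". It adds tables of shifts between percentile categories from Baseline to each of those visits, by weight-categorized dose group. The cuts are 5/25/50/75/95 for height and weight and 5/85/90/95/97 for BMI.

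SAP 6.3.1 picks the L, M and S values by sex and by age when the measurement was taken, so the row changes as the participant ages. SAP 6.3.2.1 sets the precision of that age: "In this study, age is recorded in years at each visit where the weight and height are recorded". It then fixes the row: "LMS values for a 12 year-old correspond to the half-year timepoint". SAP 6.3.2.2 applies the same rule to height, where the parameters "were mapped to the chart values corresponding to the half-year time point for that year, with respect to sex", and SAP 6.3.2.3 does so for weight. SAP 6.3.2.1 also says that the source chart is tabulated by month.

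Tables 6-6, 6-7 and 6-8 each hold six rows per sex, for ages 12 to 17. Protocol 5.1 admits participants from 12 to under 18 years, and Protocol 4.1 provides for participants who turn 18 during the study. The blood-pressure criteria in SAP 6.1.9.2 have a separate rule above age 17; the growth percentiles have none. SAP 5.1.1.7.4 rules out imputation of growth data.

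**The concern.** One row covers a full year of age. Completed years are not named, but no other reading fits scoring a 12-year-old at 12.5 years. Everyone aged 12.0 to just under 13.0 is compared with the 12.5-year reference, and at the 13th birthday the comparison moves to 13.5 years. Adolescents grow quickly enough for that step to matter: in Table 6-7 the male median height rises 7.69 cm between those two rows, which is about one reference standard deviation (152.66 × 0.0503 = 7.67 cm). Between birthdays the reference stands still while the child grows, so the percentile drifts upward.

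A shift table is read as showing which children changed growth channel. Here some of the shifts only reflect where a birthday fell. With at least 40 participants in four weight-categorized dose groups (10 per group on average), a few artificial shifts can dominate a cell. Separately, a participant who is 18 or over at a visit has no row, and the SAP does not say what then happens.

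**Working it through.** **Mapping reproduced.** Row month = (age + 0.5) × 12 + 0.5. For ages 12 to 17 this gives 150.5, 162.5, 174.5, 186.5, 198.5 and 210.5, as in Tables 6-6 to 6-8.

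**Birthday step.** The SAP's formula is z = ((X/M)^L − 1)/(L × S). Take a boy exactly on the median at 13.0 years, interpolating between the rows: X = (152.662 + 160.349)/2 = 156.51 cm.
- Age-12 row (L 0.532, M 152.662, S 0.0503): z = +0.498, 69th percentile.
- Age-13 row (L 1.233, M 160.349, S 0.0499): z = −0.479, 32nd percentile.

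This is the most extreme birthday. At the 17th birthday the median boy goes from 53.3 to 46.7.

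Share of the reference population whose category changes at each birthday:

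| Measure | 13th | 14th | 15th | 16th | 17th |
|---|---|---|---|---|---|
| Height, boys | 95% | 92% | 74% | 42% | 21% |
| Height, girls | 80% | 40% | 18% | 9% | 5% |
| Weight, boys | 72% | 68% | 61% | 50% | 37% |
| Weight, girls | 54% | 43% | 32% | 22% | 16% |

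For BMI the share is about 7 to 13%.

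**Baseline to Week 16.** Each simulated child keeps the same true z. L, M and S are interpolated linearly between the SAP rows. Baseline ages are uniform over 12.5 to 17.2 years, the span the rows can interpolate. The true rate of category change is 0%.

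| Measure | Boys: any change (down / up) | Girls: any change (down / up) |
|---|---|---|
| Height | 32% (16 / 15) | 13% (7 / 6) |
| Weight | 25% (13 / 12) | 14% (8 / 7) |
| BMI | 5% (3 / 2) | 4% (2 / 2) |

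**Net direction.** For height in boys the mean z change is −0.41 when a birthday is crossed and +0.18 when it is not. About 33% of this simulated group cross one, so the net is 0.327 × (−0.407) + 0.673 × 0.180 = −0.01. For girls it is also −0.01.

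**No reference row.** A visit falls weeks × 7/365.25 years after Baseline: 1.23 years at Week 64 and 2.38 at Week 124. A row exists only below age 18, so the Baseline age limits are 18 − 1.23 = 16.77 and 18 − 2.38 = 15.62 years. The documents give no age distribution, so the shares are a range.

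| Assumed entry ages | Week 64 | Week 124 |
|---|---|---|
| Uniform, 12 to <18 | 1.23/6 = 20% (about 8 of 40) | 2.38/6 = 40% (about 16 of 40) |
| Weighted to younger ages (6 to 1 by year of age) | 7% | 20% |
| Weighted to older ages (1 to 6) | 34% | 60% |
| Uniform, 14 to <18 | 31% | 59% |

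At Week 16 the uniform figure is 0.31/6 = 5%. All shares are before withdrawals.

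**The case against.** The strongest reply is that the endpoint is safe. The secondary endpoint is change in height and weight, summarized as raw values and change from Baseline (Protocol 9.4.1.5, SAP 5.6.3.6.2), and it uses no growth reference. SAP 6.2 lists the height and weight shift tables as additions to the protocol, and all analyses are descriptive. This stands.

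A reader might infer that the artefact could mask or mimic a drug effect. The documents do not support that. The two components cancel to a mean z change of about −0.01, the moves are nearly symmetric, and randomization gives no reason for either dose group to be favoured. What survives is noise in small cells, plus a modest downward imbalance if the sample is young: with Baseline ages of 12.5 to 15, 26% of boys move down and 20% up in height category.

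A reader might also infer that participants reaching 18 are dropped from the tables. The SAP is silent; a programmer could reuse the age-17 row, but nothing specifies it.

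Finally, a reader might conclude from Protocol Table 1-2 that height is not measured at Week 64. The week headings and column alignment of that table did not survive text extraction, so no conclusion about the schedule is drawn.

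**Conclusion.** The concern holds for the percentile shift tables and only there. For height and weight, and mainly in boys and younger girls, a material share of the category changes shown would come from age rounding; for BMI, and for height in older girls, the effect is small. It does not amount to evidence of biased growth results. The misclassification rates rest on linear interpolation of the SAP's own rows and an assumed uniform age spread.

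The gap at age 18 or over is certain in kind, because entry age and follow-up make it unavoidable. Its size depends on an age distribution the documents do not give: large at Week 124 under every assumption tried, less certain at Week 64. The change is worth making because it is cheap and the monthly chart already exists.

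**What to change.** In SAP 6.3.1 and 6.3.2, derive age in months at each measurement and use the chart's monthly rows, or interpolate L, M and S. If only whole years were collected, use Baseline age + 0.5 year + time elapsed since Baseline. This fallback leaves up to half a year of error in age, but the error is the same at every visit; in the simulation above it cuts artificial height and weight changes at Week 16 to about 1 to 3%.

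For age 18 or over, add reference rows as far as the cited source covers them; otherwise restrict the shift tables to participants under 18. Rows for ages 18 and 19 alone would not cover everyone: the oldest participant could be just under 18 + 2.38 = 20.4 years at Week 124, and with uniform entry ages about 0.38/6 = 6% would still lack a row. In either case, show the number not evaluable at each visit.

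Use the same refined height percentile as input to the blood-pressure look-up at age 17 or less (SAP 6.3.3). That table is itself indexed by whole years, so only its height-percentile input improves.

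Cost: an edit to a SAP appendix, some programming and possibly a query for month of birth. Participants need no new procedures.
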